### Randomization:

At Visit 1 (day 0) 48 eligible participants will be randomly assigned to one of four treatment groups (A, B, C or D) by means of randomisation envelopes provided by data management.

Each subject will be assigned a unique three-digit randomisation number in ascending order, by opening the randomisation envelope with the lowest free (unassigned) randomisation number available. Randomisation should be performed as late as possible, i.e. when knowledge of the assigned treatment group becomes necessary. Only trained members of the unblinded study team will be authorised to open one envelope per subject, containing the information about the allocated treatment group.

The 48 participants will be distributed between the 4 groups using a randomisation ratio of  $14 : 14 : 12 : 8 = A : B : C : D$ , with an adequate representation of high dose, low dose and placebo subjects ( $2 : 2 : 0 : 2 = A : B : C : D$ ) within the first 6 subjects to allow for the safety evaluation after the first vaccination.

A subject will be considered enrolled once the first IMP administration has been performed according to randomisation.

## 2.5 Descriptive Analyses

Descriptive analyses of continuous variables (summary statistics) will be described with the number of non-missing observations, arithmetic mean, standard deviation ( $\pm$ SD), median, quartiles (Q1 and Q3) and range (minimum and maximum).

Descriptive analysis of continuous immunogenicity variables (i.e. tables for the GMT and GMFI) will be described with the number of non-missing observations, geometric mean, confidence intervals for the geometric mean, standard deviation of logarithmic values, median, quartiles (Q1 and Q3) and range (minimum and maximum).

Categorical variables (frequency statistics) will be described with the number of non-missing observations and percentages (%). Percentages will be calculated within each stratum on the total number of non-missing observations, if not stated otherwise.

## 2.6 Inferential Analyses

The analysis for primary endpoint will compare adverse events rates up to day 56 between treatment groups using Fisher-Freeman-Halton test. The same overall test between treatment groups will be performed for all adverse event tables in the Day 56 analysis as well as the final analysis.

The immunogenicity analysis will compare the anti-zika-rsp VNT antibody geometric mean titer (GMT) in the Per Protocol (PP) analysis population between the treatment groups. GMTs and GMT ratios will be estimated by applying an analysis of variance including the factor treatment group. This will be done using log10 transformed data and taking the anti-log of the resulting point estimates for the least squares means, least squares means differences and the corresponding 2-sided 95% CIs.

P-values will also be provided to compare GMTs between the treatment groups adjusted for multiple comparisons according to Tukey-Kramer.

For the primary immunogenicity analysis, values below the lower limit of detection are replaced by half of the limit and values above the upper limit are replaced by the upper limit.

As sensitivity analysis, an analysis of immunogenicity will be applied, that does not use such imputation. Therefore, observations will be interval-censored and GMTs will be estimated by assuming normal distribution for the log-transformed values (intervals). Values below the lower limit of detection will be left-censored at the lower limit and values above the upper limit (if applicable) will be right-censored at the upper limit.

Seroconversion rates and positivity rates will be compared between groups using Fisher-Freeman-Halton test.

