|                                   | 
 
- C: 12 participants will receive one high dose treatment with MV-ZIKA-RSP- 1 <math>\times 10^5</math> (<math>\pm 0.5</math> log) TCID50 /dose on day 0 and placebo on day 28
 
- D: 8 participants will receive placebo on day 0 and day 28
 
 
After the screening visit (V0), participants will perform three additional visits to the site. On study days 0 and 28 participants will receive the vaccination, as well as, safety assessments together with immunogenicity sample collection. On study day 56 no vaccination will be done, but safety assessments and sample collection are scheduled. Safety follow-up assessments will be done by a phone call (Visit 4) approximately 6 months (day 182) after the first vaccination. A preliminary analysis will be performed after all study subjects completed Visit 3 (day 56).
 |
| Number of Participants            | 48 healthy participants   |
| Main Inclusion Criteria           | Healthy female or male volunteers, 18 - 55 years old at screening.  |
| Investigational Medicinal Product | 
MV-ZIKA RSP, presented as a liquid frozen (Lf) formulation, is a live recombinant measles virus vaccine expressing ZIKA virus antigens; suspension for injection; administered by i.m. injection, used in two different dose levels:
 
 
- High dose: 1 <math>\times 10^5</math> (<math>\pm 0.5</math> log) TCID50
 
- Low dose: 2,5 <math>\times 10^4</math> (<math>\pm 0.5</math> log) TCID50
 
   |
| Placebo                           | Physiological saline solution (0.9% NaCl), administered by i.m. injection   |
| Duration of the Study             | Study duration per subject will be 182 days (6 months), consisting of 4 weeks treatment period (study day 0 till study day 28) and 22 weeks follow up period (study day 28 till study day 182). The overall study duration is estimated to be approximately 18 months, from study approval until reporting.   |
| Statistical Methods               | 
The primary analysis will compare adverse events rates up to day 56 between treatment groups using Fisher exact tests.
 
Solicited AEs, unsolicited AEs and SAEs will be summarized by severity and term up to day 56 in the preliminary analysis and AE up to 182 are summarized in the final analysis.
  |

|                         |  |
|-------------------------|--|

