**Safety Analysis:**

MV-ZIKA was well tolerated in this population of healthy men and women. Adverse events were predominantly mild or moderate. Only one subject experienced a severe solicited AE (fever) and five participants experienced severe unsolicited TEAEs (dysmenorrhea, arthralgia, hyperbilirubinemia, hypercholesterolemia, hyperlipidaemia and hypertriglyceridemia); all were judged unlikely or not related to IMP. No AE was judged serious.

Overall, 36 (75.0%) participants reported 200 solicited AEs and 39 (81.3%) participants reported 126 unsolicited AEs (TEAEs). The proportion of participants that experienced solicited and unsolicited AEs were higher in Group D (placebo) (100% and 87.5%, respectively) than Total ZIKA (70.0% and 80.0%, respectively). Only the proportion of participants that experienced unsolicited AEs in Group C (three high doses of MV-ZIKA [ $6 \times 10^5$  TCID50/dose]; 100%) were higher than Group D (87.5%).

Solicited local AEs occurred more frequently in participants who received MV-ZIKA than those who received placebo; more participants in Group C experienced solicited local AEs than Group A and Group B in all categories. The most frequently reported solicited local AE was injection site tenderness, followed by injection site pain. Injection site edema occurred only in Group C.

Solicited systemic AEs occurred across all treatment groups. The most frequently reported AE was headache; although the proportion of participants who experienced headache in Group D (placebo) was notably higher than any MV-ZIKA treatment group (62.5% versus 12.5–43.8%). Adverse events of myalgia, limb discomfort, rash and fever were only reported by participants who received MV-ZIKA.

The most frequently reported unsolicited AEs were nasopharyngitis and headache; the frequencies of these in participants who received MV-ZIKA were similar or less than those observed in participants who received placebo. A number of AEs were reported by participants who received MV-ZIKA but were not reported by those who received placebo. Most notably, these included general disorders and administration site conditions, and musculoskeletal and connective tissue disorders. Diarrhea was reported only by participants who received three high doses of MV-ZIKA (Group C).

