***Please note:***

*As this is a first in humans' study, the site should initially enroll a group of six participants and then pause with enrollment until these participants completed their Post Dose Safety Follow Up one week after the first vaccination. If no events as defined in section 8.9.1 "Safety Stopping Rule" are identified, the site should resume enrolling participants. If such events were identified, the investigators and the sponsor need to assess the risk of continuing the study and based on this assessment to decide if or if not, the study should be continued.*

The 48 participants will be distributed between the 4 groups using a randomisation ratio of 14 : 14 : 12 : 8 = A : B : C : D, with an adequate representation of high dose, low dose and placebo subjects (2 : 2 : 0 : 2 = A : B : C : D) within the first 6 subjects to allow for the safety evaluation after the first vaccination.

A subject will be considered enrolled once the first IMP administration has been performed according to randomisation.

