### 1.3 Endpoints

#### 1.3.1 *Primary Endpoint*

- Rate of adverse events (AEs) up to study day 56

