## 2.13 Columns in Tables

Every treatment group has its own column in the analysis and an additional total column will be added. For OV tables, where all subjects are shown, there is an additional column with subject not randomized.

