## 2.14 Changes in the Conduct of the Study or Planned Analysis

No changes to the statistical analysis as compared to CSP are planned.

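### AE rates get only a four-group p-value and no estimate against placebo; if placebo rates are again near 100%, that test has little or no power to show harm

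*Combined protocol and SAP*

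**What the plan says.** - **Endpoint.** SAP 1.3.1 gives it only as "Rate of adverse events (AEs) up to study day 56". No table or row is named as primary. Participants with any AE (first row of SAP Table 1.4.1.2) is the natural reading, but it is an inference.
- **Test.** SAP 2.6: "The analysis for primary endpoint will compare adverse events rates up to day 56 between treatment groups using Fisher-Freeman-Halton test". It continues: "The same overall test between treatment groups will be performed for all adverse event tables in the Day 56 analysis", and likewise in the final analysis.
- **Protocol wording.** The synopsis says "The primary analysis will compare adverse events rates up to day 56 between treatment groups using Fisher exact tests", without stating overall or pairwise. SAP 2.14 records "No changes to the statistical analysis as compared to CSP are planned".
- **Columns.** SAP 2.13: "Every treatment group has its own column in the analysis and an additional total column will be added". That total combines 40 vaccinees with 8 placebo recipients.
- **Contrast with immunogenicity.** The same SAP 2.6 plans ratios, 95% CIs and Tukey-Kramer comparisons for GMTs, a secondary endpoint. Nothing comparable is planned for AEs.
- **Predecessor.** Protocol 4.4.1 (MV-ZIKA-101) reports that the proportions with solicited and unsolicited AEs were "higher in Group D (placebo) (100% and 87.5%, respectively"), against 70.0% and 80.0% in all MV-ZIKA recipients.

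**The concern.** A placebo-controlled first-in-human vaccine trial should report how many more vaccinees than placebo recipients had AEs, and how precisely that is known. A four-group p-value gives neither a size nor a direction, and the planned columns do not supply an interval.

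A second issue makes the p-value fragile. If the primary variable is whether a participant had any AE over 56 days, with diaries after each injection, the placebo rate may sit close to 100%. There is then no room above it for a vaccine excess to appear. A non-significant result would say almost nothing about safety, yet it would be the only comparative inference on the primary endpoint.

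**Working it through.** The plan states no power, target difference or sample-size formula, so there is no design figure to reproduce. Alpha is not stated for AEs; 0.05 is assumed. Harm power below counts only significant tables in which the placebo rate is lower than the pooled vaccine rate.

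**1. Predecessor counts (protocol 4.4.1).** Overall, 36 participants (75.0%) had solicited AEs, so N = 36/0.75 = 48. With n on placebo, 0.70(48 − n) + 1.00n = 36, so 0.30n = 2.4 and n = 8. Check: solicited 28/40 + 8/8 = 36/48 = 75.0%; unsolicited 32/40 + 7/8 = 39/48 = 81.25%, printed as 81.3%. Since 8/8 placebo recipients had a solicited AE, any-AE there was also 8/8, although the protocol does not print that figure. The exact 95% CI for 8/8 is 63% to 100%.

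**2. Exact p-values here (A 14, B 14, C 12, D 8; protocol 8.2), all 40 vaccinees affected.**
- Placebo 8/8: only one table is possible, p = 1. With placebo at 8/8, no vaccine result can point to harm.
- Placebo 7/8: one unaffected participant, in the smallest arm, p = 8/48 = 0.167.
- Placebo 6/8: both unaffected participants in D, the least likely arrangement, p = C(8,2)/C(48,2) = 28/1128 = 0.025.

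**3. Harm power with vaccine at 100%.** Significance needs at most 6 affected of 8 on placebo, so for placebo rate π, power = 1 − 8π⁷(1 − π) − π⁸.
- π = 0.875: 1 − 0.393 − 0.344 = 0.26.
- π = 0.75: 1 − 0.267 − 0.100 = 0.63.
- At π = 0.60 and 0.50 the same formula gives 0.89 and 0.97.

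**4. Harm power in other scenarios**, by enumerating all 15 × 15 × 13 × 9 = 26,325 tables. The rates are assumptions. Pooled means Fisher's exact test, 40 v 8.

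| Vaccine A/B/C v placebo | Overall test | Pooled |
|---|---|---|
| 97/95/95% v 87.5% | 0.119 | 0.096 |
| 99% in each arm v 87.5% | 0.215 | 0.199 |
| 95/90/90% v 75% | 0.229 | 0.240 |
| 80% in each arm v 37.5% | 0.51 | 0.63 |
| 90/40/60% v 37.5% | 0.73 | 0.22 |
| 50/10/30% v 0% | 0.72 | 0.18 |

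Near the ceiling the two tests are about equally weak. Away from it, pooling gains when the arms share a rate and loses heavily when they differ.

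**5. What an estimate would add (Newcombe 95% CI, vaccine minus placebo).**
- 40/40 v 8/8: 0 points (−8.8 to +32.4), where the test gives p = 1.
- 38/40 v 7/8: +7.5 points (−7.9 to +42.3).
- 28/40 v 8/8, the predecessor's solicited counts: −30 points (−45.4 to +4.6).

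**The case against.** The strongest reply is that the plan is reasonable for a small descriptive trial.

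- It claims no power. An overall test suits a dose-finding design with two dose levels and one- or two-dose regimens, and step 4 shows it can clearly beat pooling when arms differ. This stands.
- Related, severe, serious and medically attended AEs, and AEs by symptom and term, are already tabulated by arm and tested. Placebo has its own column, so a reader can subtract. This stands too; what is missing is the difference with its interval.
- Safety decisions during the trial rest on the pause after six participants and the stopping rules, not on this p-value. This also stands.
- With n = 8 the intervals will be wide. That is true, and it is a reason to show them.

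Three stronger readings are tempting, and the documents do not support them:

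- **That the test cannot show harm.** It can if placebo is 6/8 or lower and nearly all vaccinees are affected. The predecessor's 8/8 came from a different vaccine, three injections and a treatment period to day 84; here there are two injections and the endpoint runs to day 56. Its vaccinees were at 70.0% and 80.0%, so saturation in every arm was not seen.
- **That the overall test is the fault and a pooled test the cure.** Step 4 contradicts this.
- **That the SAP silently departed from the protocol.** The protocol's wording is compatible with one overall test per table. Nor does either document say that a non-significant result will be taken as equal safety.

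**Conclusion.** The point holds as a gap in estimation, with a conditional weakness in the test. No excess of AEs over placebo is estimated with a confidence interval for the primary safety endpoint or any other AE table.

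If placebo rates are again near 100%, the planned test has little or no power to show harm: none at placebo 8/8, about 12% to 21% for vaccine rates of 95–99% against 87.5%, and 23% for 90–95% against 75%. At 100% against 75% it is 63%, so the weakness depends on the ceiling recurring.

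This rests on three assumptions: alpha of 0.05, participants with any AE as the primary variable, and the scenario rates. The limits are the ceiling and eight placebo recipients. This is a worthwhile, inexpensive improvement rather than a flaw that invalidates the plan.

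**What to change.** In SAP 2.6, 2.13 and 6.2:

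1. Name the primary AE variable and its table row.
2. Keep the Fisher-Freeman-Halton test as supportive, and say that it is how the protocol's Fisher exact tests are to be read.
3. Add an any-MV-ZIKA-RSP column (A + B + C, n = 40).
4. Report risk differences with 95% CIs suited to small samples, for each vaccine arm v D and pooled vaccine v D. Do this for any AE and for the related, solicited and severe (grade 3 or higher) AEs already tabulated. Per-arm estimates are needed because pooling can hide differences between arms.
5. Base the safety conclusion on these estimates, and state that a non-significant p-value is not evidence of equal safety.

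The cost is SAP wording and table programming, with no new data, visits or participants. The downside is more comparisons, to be labelled as descriptive estimation without multiplicity control, and wide intervals because n = 8.

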**Doses (volumes administered):**

| Group | Treatment  |
|-------|--|
| A     | MV-ZIKA 0.6 mL ( $6 \times 10^5$ TCID 50 /dose)
Placebo 0.6 mL |
| B     | MV-ZIKA 0.1 mL ( $1 \times 10^5$ TCID 50 /dose)                   |
| C     | MV-ZIKA 0.6 mL ( $6 \times 10^5$ TCID 50 /dose)                   |
| D     | Placebo 0.6 mL   |

The phase I clinical batch of this vaccine was present at a ready to use liquid formulation at a single concentration.

The mean (SD) age of participants in the safety/mITT population was 36.8 (10.7) years and 47 (97.9%) participants were Caucasian/White. The proportion of males (20 [41.7%]) was smaller than that of females (28 [58.3%]). Of the 28 females, 24 (85.7%) participants were of

childbearing potential. Demographic data for the PP population were similar to the safety/mITT population.

Participants were enrolled into the study from May to October 2017.

Immunogenicity Analysis:

The primary endpoint was immunogenicity on Study Day 56 confirmed by the presence of functional anti-zika antibodies as determined by a neutralizing antibody assay. An increase in Zika neutralizing antibody GMT was observed only in Group C (three high doses of MV-ZIKA [ $6 \times 10^5$  TCID50/dose]). The largest increase in neutralizing antibody GMT occurred after the second vaccination, increasing from 6.6 to 7.9; no increase occurred after the first vaccination and a reduction of 0.7 was observed after the third vaccination. No statistically significant difference was detected between Group C and placebo. The Group A regimen of one high dose of MV-ZIKA ( $6 \times 10^5$  TCID50/dose) and two placebos showed no increase in GMT. The Group B regimen of three low doses of MV-ZIKA showed no notable differences when compared with placebo (Group D). Assessment of the effect of baseline measles titer on GMT of neutralizing antibodies at Day 56 showed no effect.

Seroconversions were primarily observed in participants who received high dose MV-ZIKA ( $6 \times 10^5$  TCID50/dose). Overall, seven participants (one in Group A, one in Group B, and five in Group C) showed seroconversion after MV-ZIKA vaccination and one after placebo. Variations in seroconversion across all treatment groups during the study did not achieve statistical significance.

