| Version 2.1 (28 Sep 2020) |  |   |
| 1.                        | PRNT 50 was replaced with VNT.  | A Plaque Reduction Neutralization Test method was replaced with another, highly similar serum sample test termed Virus Neutralization Test.   |
| 4.5                       |  |   |
| 5.2                       |  |   |
| 6.1                       |  |   |
| 6.2.2                     |  |   |
| 6.5                       |  |   |
| 8.5.1                     |  |   |
| 8.5.3                     |  |   |
| 8.5.4                     |  |   |
| 8.11.2                    | Description of usage of a Plaque reduction neutralization assay was replaced with description of usage of a Virus Neutralization Test. |   |
| 8.11.4                    | PRNT 50 was replaced with VNT.  |   |
| 12.2                      |  |   |
| 12.2                      | Seroconversion will be defined as anti-zika-rsp VNT titres $\geq 20$ 10.   | Neutralizing antibodies were quantified with a slightly different assay than originally planned. This VNT has a Lower Limit of Quantification (LLOQ) of 20, requiring us to adapt the protocol to accommodate the more stringent cut-off. |

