### 5.2 Derivations and Definitions

- For final analysis all time points, including Visit 1 (Day 0), Visit 2 (Day 28) and Visit 3 (Day 56) will be analyzed.
- Seroconversion rate for anti-zika-rsp VNT titers is defined as proportion of subjects achieving anti-zika-rsp VNT titers  $\geq 20$  at a certain time point.

- Seroconversion rate for anti-zika-rsp ELISA titers is defined as 4-fold increase over baseline (Visit 1 –Day 0). If no Visit 1 (Day 0) sample is available, no seroconversion will be determined.
- For MV ELISA, Zika ELISA, NT and T-Cell an analysis of positive versus negative values is planned. Since such a definition could not be discussed and communicated with the central laboratory at the time of generation of this SAP, details about used limits will be shown as footnotes in the corresponding tables and explained in the Clinical Study Report.
- For the different immunogenicity parameter there are different lower limit of quantification (LLOQ). [redacted]
  - In data listings, the original reported value “<LLOQ” will be displayed.
  - For calculations (GMT, median...) the half of the true LLOQ value will be used for such values.
  - If another unexpected value is reported as LLOQ in the data than mentioned here, the half value of the reported LLOQ will be used for the calculations.
- For the different immunogenicity parameters there are different upper limits of quantification (ULOQ) [redacted]
  - In data listings, the original reported value “>ULOQ” will be displayed.
  - For calculations (GMT, median...) the ULOQ value will be used for such values.
  - If another unexpected value is reported as ULOQ in the data than mentioned here, this ULOQ value will be used for calculations.
- For analysis using interval-censored data an interval will be defined for every observation. Observations between LLOQ and ULOQ will be handled as interval with left limit and right limit being the observed value. For values <LLOQ the interval will be left-censored with the LLOQ as right limit. For values >ULOQ the interval will be right-censored with the ULOQ as left limit.

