| 1.2.1.5   | 2.2.1.5         | Concomitant Medications by ATC Level 2 and 3 (Safety Population)                         |  |
| 1.2.1.6   | n/a             | Vital Signs at Baseline (Safety Population)  | 
 
• Systolic blood pressure [mmHg]
 
• Diastolic blood pressure [mmHg]
 
• Pulse rate [beats/min]
 
  |

Adapted from:

Page 23 of 33

STAT03\_A Statistical Analysis Plan

Version 6.0, Effective Date 16-Feb-2018

Confidential and intellectual property of Assign DMB. No part of this document or its contents may be duplicated, referenced, published or otherwise disclosed in any form or by any means without prior written consent of Assign DMB.

|  |                 |  |   |
|--|-----------------|--|---|
|  |                 |  | 
 
• Temperature [C]
 
 |
| 1.2.2.1-1.2.2.6  | 2.2.2.4-2.2.2.5 | For preliminary analysis repeat tables 1.2.1.1-1.2.1.6 and for final analysis tables 2.2.1.4-2.2.1.5 for mITT population (if not the same as Safety Population). |   |
| NOTE: Prior/Concomitant Medication tables will also be provided for final analysis but including all Prior/Concomitant Medications reported during the study |                 |  |   |
| Immunogenicity Analysis   |                 |  |   |
| Zika-RSP VNT Antibody   |                 |  |   |
| n/a  | 2.3.1.1         | GMT of Zika-RSP VNT Antibody by Visit (mITT Population)  |   |
| n/a  | 2.3.1.2         | GMT of Zika-RSP VNT Antibody based on interval-censored data by Visit (mITT Population)  |   |
| n/a  | 2.3.1.3         | ANOVA for GMT of Zika-RSP VNT Antibody between treatment groups by Visit (mITT Population)   |   |
| n/a  | 2.3.1.4         | Seroconversion rate for of Zika-RSP VNT Antibody by Visit (mITT Population)  |   |
| n/a  | 2.3.1.5         | Positivity of Zika-RSP VNT Antibody by time point  |   |
| Zika-RSP ELISA Antibody   |                 |  |   |
| n/a  | 2.3.1.6         | GMT of Zika-RSP-ELISA Antibodies by Visit (mITT Population)  |   |
| n/a  | 2.3.1.7         | GMT of Zika-RSP-ELISA Antibodies based on interval-censored data by Visit (mITT Population)  |   |
| n/a  | 2.3.1.8         | ANOVA for GMT of Zika-RSP-ELISA Antibodies between treatment groups by Visit (mITT Population)   |   |
| n/a  | 2.3.1.9         | Seroconversion rate of Zika-RSP-ELISA Antibodies by Visit (mITT Population)  |   |

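### Between-arm VNT titre ratios are computed only on half-LLOQ substituted data; the planned interval-censored analysis stops at per-arm GMTs (minor)

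*Combined protocol and SAP*

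**What the plan says.** The limit is given in the protocol's Revision Index (section 20, Version 2.1): "This VNT has a Lower Limit of Quantification (LLOQ) of 20". The seroconversion cut-off in protocol 12.2 and SAP 5.2 is also a titre of at least 20.

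SAP 2.6 sets the rule for the primary immunogenicity analysis: "values below the lower limit of detection are replaced by half of the limit". SAP 5.2 repeats it for GMTs and medians: "the half of the true LLOQ value will be used for such values". Section 2.6 speaks of a detection limit and section 5.2 of the LLOQ; I take both to mean 20 for the VNT. The assay limits in SAP 5.2 are redacted.

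The comparison between arms is also in SAP 2.6: "GMTs and GMT ratios will be estimated by applying an analysis of variance including the factor treatment group", on log10 titres, with 2-sided 95% CIs and Tukey-Kramer p-values. Its VNT output in SAP 7.1 is table 2.3.1.3, "ANOVA for GMT of Zika-RSP VNT Antibody between treatment groups by Visit (mITT Population".

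SAP 2.6 then adds a sensitivity analysis without substitution, in which "observations will be interval-censored and GMTs will be estimated by assuming normal distribution for the log-transformed values (intervals". SAP 5.2 defines the intervals. SAP 7.1 lists it as table 2.3.1.2, "GMT of Zika-RSP VNT Antibody based on interval-censored data by Visit (mITT Population", with tables 2.3.1.7 and 2.3.1.12 for the two ELISAs, and all are repeated for the PP population. The ANOVA tables 2.3.1.3, 2.3.1.8 and 2.3.1.13 have no censored counterpart.

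**The concern.** SAP 1.1.2 says the optimal dose will be evaluated on safety, tolerability and VNT immunogenicity. The GMT ratios A:B, A:C and B:C are the only pairwise VNT contrasts the plan specifies; the seroconversion test in SAP 2.6 is an overall test across groups.

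The only human neutralising titres in the documents are low. In the predecessor study (protocol 4.4.1) the arm with the largest rise had a GMT "increasing from 6.6 to 7.9". If titres here were in that region on the same scale, most values would be replaced by 10 and each arm's GMT would be largely that constant. Ratios between such arms would look close to 1 whatever the true difference, which favours a conclusion that dose or number of doses does not matter.

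**Working it through.** The plan states no effect size, power or titre SD, so there is no figure of its own to reproduce. The arm sizes are 14, 14, 12 and 8 (sum 48).

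**Inputs.** The LLOQ is 20 (protocol 20), so L = log10 20 = 1.3010. The substituted value is 10, or 1 on the log10 scale. Assumptions: log10 titres are normal with mean μ and SD σ, with σ from 0.15 to 0.6, and the GMT pairs are scenarios. The documents give neither.

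**Formula.** With z = (L − μ)/σ, p = Φ(z) is the share below 20. The expected reported log10 titre is p·1 + μ(1 − p) + σφ(z). The reported ratio is 10 to the power of the difference between two arms.

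**Both arms below the limit: 16 against 8, σ = 0.4**
- GMT 16: μ = 1.2041, z = 0.2423, p = 0.5957, φ = 0.3874. Reported: 0.5957 + 1.2041 × 0.4043 + 0.4 × 0.3874 = 1.2375, a GMT of 17.28.
- GMT 8: μ = 0.9031, z = 0.9949, p = 0.8401, φ = 0.2432. Reported: 0.8401 + 0.9031 × 0.1599 + 0.4 × 0.2432 = 1.0818, a GMT of 12.07.
- The true ratio of 2.00 is reported as 17.28/12.07 = 1.43.

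**Arms at and above the limit: 40 against 20, σ = 0.2**
- GMT 40: μ = 1.6021, z = −1.5051, p = 0.0661, φ = 0.1285. Reported: 1.5879, a GMT of 38.72.
- GMT 20: μ = 1.3010, z = 0, p = 0.5, φ = 0.3989. Reported: 0.5 + 0.6505 + 0.0798 = 1.2303, a GMT of 16.99.
- The true ratio of 2.00 is reported as 38.72/16.99 = 2.28. With a small SD, the censored half of the lower arm sits just under 20, so setting it to 10 pulls that arm down too far.

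**Range over σ = 0.15 to 0.6**

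| True GMTs | True ratio | Reported ratio | Below 20, first arm | Below 20, second arm |
|---|---|---|---|---|
| 7.9 : 6.6 | 1.20 | 1.00–1.07 | 75–100% | 79–100% |
| 12 : 7.9 | 1.52 | 1.06–1.22 | 64–93% | 75–100% |
| 16 : 8 | 2.00 | 1.26–1.44 | 56–74% | 75–100% |
| 20 : 10 | 2.00 | 1.51–1.60 | 50% | 69–98% |
| 25 : 15 | 1.67 | 1.42–1.84 | 26–44% | 58–80% |
| 40 : 20 | 2.00 | 1.73–2.43 | 2–31% | 50% |
| 80 : 40 | 2.00 | 1.89–2.09 | 0–16% | 2–31% |

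**Would the planned censored model help?** It was simulated with treatment group as a factor, vaccine arms of 14, 14 and 12, and σ = 0.4. For 16:8 the median estimated ratio was 1.41 with substitution and 1.93 with the censored model. For 12:7.9 the censored estimate was more variable: the root mean squared error of the log10 ratio was 0.18, against 0.13 with substitution. In about 12% of those runs an arm had no quantifiable value; this share depends on what is assumed for the third arm.

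**The case against.** **Censoring is already addressed.** A reader might infer that the SAP ignores the assay limit and that dose differences will be hidden. The documents do not support that. SAP 2.6 plans an analysis without substitution, and the ratio of two censored GMTs follows by division. What is missing is the CI and p-value for that ratio.

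**Seroconversion is untouched.** Its cut-off equals the LLOQ, so the substituted value cannot change it, and the rates per arm in table 2.3.1.4 already give one minus the share below 20. This stands, although the test is not pairwise.

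**The 7.9 is a weak anchor.** A reader might take it as the titre to expect here. Protocol 4.4 calls the predecessor a different vaccine, and protocol 4.4.1 names neither its neutralisation assay nor its limit, so a common titre scale is not established. Protocol 4.3.2 reports high neutralising antibody levels in all primates given 1×10^5 TCID50 of the present construct. The 7.9 shows a possibility only.

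**The bias has no fixed direction.** This is correct, as 40:20 shows. It limits the claim of attenuation to arms mostly below 20, but it does not make the substituted ratio safe.

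**The censored model is no clear winner.** Under heavy censoring it is more variable and sometimes gives no ratio, because the assay has removed the information. This stands against making it the lead analysis. It does not argue against showing it.

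**The stakes are modest.** This is a secondary endpoint in a phase I trial with no formal sample size. At SD 0.5, Tukey power for a two-fold A:B difference is only 0.14 to 0.16 even without censoring, so low power there comes mainly from the arm sizes.

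**Conclusion.** The point holds in a limited form and is minor. Every between-arm VNT estimate that carries a CI rests on half-LLOQ data, and the analysis that avoids the substitution stops one step short of the comparison.

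The size depends on where the titres fall. With both arms mostly below 20, a true two-fold ratio (16:8) is reported as 1.26 to 1.44. At 40:20 it can be reported as anything from 1.73 to 2.43, depending on the SD, and at 80:40 the distortion is small (1.89 to 2.09). These figures assume log-normal titres and SDs that the documents do not give. The documents do not show which region applies to this vaccine on this assay.

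**What to change.** In SAP 2.6, extend the planned interval-censored normal model by fitting treatment group as a factor. Report VNT GMT ratios with 95% CIs and Tukey-adjusted p-values beside the half-LLOQ ANOVA. In SAP 7.1, add a censored counterpart to table 2.3.1.3 for mITT and its repeat for PP.

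State that dose and schedule conclusions will draw on both analyses when a material share of either arm is below 20, and define that share before the titres are analysed. Where an arm has no quantifiable value, report its GMT as below 20, give no ratio, and rely on the seroconversion rates. No new table for the share below 20 is needed, and the ANOVA can keep its place.

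The cost is SAP wording and one more model output. Under heavy censoring the added CIs will be wide or not estimable.
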